- Use as "screening failure" data by members of the study team
- Provide to others outside of the research team (with the participant's permission)
- Request permission from participant to maintain and use the identifiable information
- Other

2. * Will participants be able to withdraw their data (paper, electronic, or specimens) from the study (e.g. ask that it be destroyed or returned) if they no longer wish to participate? (FDA-regulated studies should select No see help text)

- Yes
- No

3. * What will happen to the research materials (e.g. data, specimens, documents, etc.) when the research has been completed?

- Stored indefinitely with identifiers removed
- Stored indefinitely with identifiers attached
- Destroyed at the end of study once the minimum time required for data retention has been met per VCU Data Retention Policy and/or sponsor retention requirements**
- Destroyed when notified by sponsor but not less than the minimum time required for data retention per VCU Data Retention Policy
- Other

ID: MS12_HM20027241

View: SF2 - Sharing Plan

Sharing Plan

This page addresses times when investigators may be required to share information about participants or may desire to share their research information/specimens with the aim of advancing science. This page creates a plan for when

and how information/specimens should be shared.

Try to anticipate all reasonably foreseeable sharing so that the consent document can also reflect that information. However, it is acceptable to amend this page later and explain either how re-consent of previously and currently enrolled participants will occur or why re-consent should not be required.

The IRB reviews this page against the consent document (if one exists) to demonstrate the ethical principle of Respect for Persons by confirming that plans for sharing do not go against what participants would understand about the use of their data/specimens.

The IRB also ensures there are adequate protections for the privacy of participants and the confidentiality of participants' data/specimens when data is shared with others.

1. * Is it likely investigators could discover information about child/elder abuse or neglect that would require mandatory reporting by the investigators or staff?

The Code of Virginia requires that most medical personnel and all employees of institutions of higher education report suspected child/elder abuse or neglect.

- Yes
 No

2. * Is it likely investigators could discover a previously unknown reportable disease or condition that would require mandatory reporting by the investigators or staff (i.e., HIV, coronavirus, hepatitis, etc.)?

- Yes No

3. * Will the sponsor or investigator obtain a Certificate of Confidentiality for this study?

Certificates of Confidentiality (CoC) are issued by the National Institutes of Health (NIH), the FDA and CDC to protect identifiable research information from forced disclosure. All human subject research studies regardless of funding can qualify to receive a CoC. A CoC is automatically issued for research that was ongoing on December 13, 2016, or initiated after that date. For more information, see <https://humansubjects.nih.gov/coc/>

- No Will not obtain CoC for this study
 Yes CoC has been obtained or issued automatically
 Yes CoC request is pending

4. * Select the way(s) that information or biospecimens (including DNA) may be used by the VCU PI or VCU study team for other future research projects (i.e. analyses beyond/apart from the aims of this study)?
See help text for definitions.

Will use directly identifiable information or specimens.

(Directly identifiable means that identifiers like name, medical record number, social security number, etc. are included in/attached to the dataset/specimens. Maintaining identifiable data for future research is treated as a registry by the VCU IRB. The IRB must approve the new research use in an amendment to this study or as part of a new study before the project is initiated. VCU IRB studies will be asked more questions about this on a later page)

Will use de-identified or indirectly identifiable information or specimens.

(De-identified means that a linkage/key code exists that links identifiers to data/specimens. When the researcher holds both the data and the key, the VCU IRB considers the subjects to be readily identifiable. Maintaining identifiable data for future research uses is treated by the IRB as a registry. The IRB must approve the new research use in an amendment to this study or as part of a new study before the project is initiated. VCU IRB studies will be asked more questions about this on a later page)

Will use anonymized information or specimens.

(‘Anonymized’ means that 1) no linkage/key codes exist that link identifiers to data/specimens; and 2) subjects cannot be readily identified, i.e. no direct or indirect identifiers or identifiable combinations of variables. The VCU IRB considers uses of anonymized data/specimens to not be human subject research.)

Will use aggregate results (summary-level results), not individual-level information or specimens.

- (The VCU IRB considers uses of aggregate data to not be human subject research because there are no individual subjects.)*

Will contribute to an existing registry or repository

- (VCU IRB studies will be asked more questions about this on a later page.)*

- Will not use information/specimens for purposes beyond this study.

- Not sure and will submit an amendment when known

- Other use(s) of individual-level information in a way not listed above

5. * Select the way(s) the VCU PI/study team may share information or biospecimens (including DNA) with other researchers who are not on this study team (i.e. for analyses beyond/apart from the aims of this study).
See help text for definitions.

Will share directly identifiable information or specimens with other researchers.

(Directly identifiable means that identifiers like name, medical record number, social security number, etc. are included in/attached to the dataset/specimens. Maintaining identifiable data for future research uses is treated by the VCU IRB as a registry. The data recipients use of identifiable data would require them to obtain IRB review. VCU IRB studies will be asked more questions about this on a later page.)

Will share de-identified or indirectly identifiable information or specimens with other researchers.

- (De-identified means that a linkage/key code exists that links identifiers to data/specimens. The VCU researcher maintains the key but does not share it with any other researchers. The recipients use of de-identified data/specimens may not be human subject research if there is documentation that the key will never be shared with the recipient, but they should check with their own IRB about review requirements. VCU IRB studies will be asked more questions about this on a later page.)*

Will share anonymized information or specimens with other researchers.

- (‘Anonymized’ means that 1) no linkage/key codes exist that link identifiers to data/specimens; and 2) subjects cannot be readily identified (i.e. no direct or indirect identifiers or identifiable combinations of variables). The VCU IRB considers uses of anonymized data/specimens by other researchers to not be human subject research, but the recipient should check with their own IRB about review requirements.)*

Will only share aggregate results (summary-level results), not individual-level information or specimens.

- (The VCU IRB considers uses of aggregate data to not be human subject research because there are no individual subjects. The data recipient should check with their own IRB about review requirements.)*

- Will contribute to an existing registry or repository (VCU IRB studies will be asked more questions about this on a later page.)
- Will submit data to an NIH genomic data repository (VCU IRB studies will be asked more questions about this on a later page.)
- Will not share information/specimens with other researchers.
- Not sure and will submit an amendment when known
- Other sharing of individual-level information with other researchers

6. * The Principal Investigator certifies that after the study has been closed with the VCU IRB, the following conditions will be met whenever individual level research information and/or specimens are used or shared:

- The identities of participants who are represented in the dataset/specimens will not be readily ascertainable or otherwise re-identifiable by the recipient;
- If a linkage/code key is created, it will be maintained at VCU and not shared with the recipient under any circumstances;
- The PI will have no knowledge that the remaining information could be used alone or in combination with any other information to identify the individuals represented in the data; and
- The PI agrees to abide by this sharing plan even after the study has been closed with the VCU IRB.

- Yes
- No
- N/A - No sharing will occur

ID: MS12_HM20027241 View: SF2 - Pertinent Results and Incidental Findings

Pertinent Results and Incidental Findings

1. * Is it likely investigators could discover a participant’s previously unknown condition (e.g. pregnancy, disease, suicidal thoughts, wrong paternity, genetic results, or other findings that may be of importance to health or well-being) or if a participant is engaging in illegal or reportable activities:

- Yes
- No

ID: MS12_HM20027241 View: SF2 - Risk Benefit Complete

Risk Benefit Complete

- Protocol Progress:
- ? INITIAL SETUP
 - ? BACKGROUND, RATIONALE & GOALS
 - ? RESEARCH PLAN
 - ? CONSENT PLAN
 - ? RISKS, PRIVACY & CONFIDENTIALITY
 - ? POPULATIONS WITH SPECIAL CONSIDERATIONS
 - ? INSTITUTIONAL REQUIREMENTS
 - ? DOCUMENTS

Click Continue below to go to the next section

ID: MS12_HM20027241 View: SF2 - Populations with Special Considerations

Populations with Special Considerations

1. * Check all participant groups that will be either

a) Specifically included in this study or

b) Discernable in the research data/specimens.

(Selections will branch)

- Children
- Emancipated minors
- Wards of the State
- Pregnant women or fetuses
- Neonates or Post-delivery Materials
- Prisoners
- Decisionally Impaired Adults**
- VCU / VCUHS students or trainees
- VCU / VCU Health System employees**
- Individuals with limited English proficiency
- Active military personnel
- Student populations in K-12 educational settings or other learning environments
- Members of a federally recognized American Indian and Alaska Native tribe
- None of the Above

2. Additional considerations for VCU/VCU Health System employees:

* Describe how the study will minimize the possibility of coercion to participate.

VCU nurses, physicians, and APPs ("healthcare providers") will be invited to complete a survey at the end of a patient's participation in the study. The survey does not contain any sensitive information. Healthcare providers will be approached and asked if they are willing to complete a survey using the study iPad. Within the survey, information will clearly state the their willingness to complete the survey is completely voluntary. The survey will in no way be linked to the healthcare provider so there is no record of whether individual providers completed the survey or not.

ID: MS12_HM20027241

View: SF2 - Decisionally Impaired Adults

Decisionally Impaired Adults

1. * Choose the nature of the decisional impairment participants will have:

- Temporarily Incompetent to Give Consent**
- Permanently Incompetent to Give Consent
- Unknown

2. * Explain why this population is necessary for the conduct of the study.

ICU patients most at risk for development of delirium are crucial to answering the aims of this study. It is common for ICU patients to have limited decisional capacity during their ICU level of care due to their medical conditions and/or sedative medications they are receiving. Decisional impairment for ICU patients may be temporary (i.e., resolves when sedating medication is decreased or removed) or permanent (i.e., the mechanism of their medical conditions is permanent in nature).

3. * Describe methods for determining whether participants are capable of providing consent or assent.

The study team will determine consent capability by utilizing a primary method, followed by a secondary confirmation. To obtain primary determination, the study team will examine the patient's EHR documentation of neurological status. Per the EHR, is the patient alert and orientated? If yes, the study team member obtaining consent will proceed to the patient's bedside. During the informed consent discussion, the study team member will pay close attention to any actions and/or communication from the patient that is not in alignment with the patient's documented mental status. If there are ever any doubts, the LAR will be sought for primary consent with patient assent.

4. * If a participant is capable of exercising some judgment concerning the nature of the study, describe how assent will be obtained.

Three scenarios are possible. If the patient is awake and capable of signing, a signature of assent will be asked from the patient following LAR consent. If the patient is awake but not able to sign, the patient will be asked to give some sign of assent (i.e., head nod yes, thumbs up). However, there is a case where patient assent may not be possible, and therefore, the study team will need to solely rely on LAR consent only. This situation would be related to a patient that has a medical condition or sedation that prevents their alertness.

5. Describe, if applicable, how the individuals' ability to give consent will be assessed throughout the study and how consent will be obtained when appropriate.

Throughout the study, continual assent will be assessed by members of the study team. At any point the patient's assent does not seem clear, the patient will be withdrawn from the study.

6. * Describe how and when consent will be obtained from participants' legally authorized representative (LAR).

Consent will be sought from the patient's LAR when the patient is not able to fully consent for themselves.

ID: MS12_HM20027241

View: SF2 - Populations with Special Considerations Section Complete

Populations with Special Considerations Section Complete

Protocol Progress:

- ? INITIAL SETUP
- ? BACKGROUND, RATIONALE & GOALS
- ? RESEARCH PLAN
- ? CONSENT PLAN
- ? RISKS, PRIVACY & CONFIDENTIALITY
- ? POPULATIONS WITH SPECIAL CONSIDERATIONS
- ? INSTITUTIONAL REQUIREMENTS
- ? DOCUMENTS

Click Continue below to go to the next section

ID: MS12_HM20027241

View: SF2 - Study Funding

Study Funding

1. * Have you applied for funding:

- Yes
 No

2. Is this study already funded:

- Yes
 No

3. * Select all funding sources for this study (pending or awarded):

- Industry
 Direct Federal
 Indirect Federal
 State/Local Government
 Non-Profit - Sponsored Project
 Non-Profit - Gift
 Internal Grant
 Investigator/Departmental Funds
 None
 Other

4. * In addition to providing funding support, what is the funding sources role in this study? Select all that apply:

- Solely providing funding support**
 Providing resources (e.g. study drug, device)
 Providing guidance to the researcher but does NOT make decisions about study design
 Study design/Creation of the study protocol
 Collaborator in the research (helps design and/or conduct the study) [list the funder as a site on the Types of Sites page]
 Data or sample analysis regardless of identifiability

5. Select all related funding proposals and contracts that have been submitted through the Division of Sponsored Programs (DSP):

RAMS-SPOT ID# (FP/PT/PD#)	Direct Sponsor	PI Title	Status	Start	End
---------------------------	----------------	----------	--------	-------	-----

There are no items to display

ID: MS12_HM20027241

View: SF2 - Types of Sites

Types of Sites

VCU Site Information

1. * Select all VCU sites that will be utilized in this study:

- Children's Hospital of Richmond at VCU
 Clinical Research Services Unit (CRSU)
 Massey Cancer Center
 VCU Health Community Memorial Hospital
 VCU Health Tappahannock Hospital
 VCU Medical Center
 Other VCU Health Location
 VCU Monroe Park Campus
 VCU Qatar

Other VCU Site

Non-VCU Site Information

Non-VCU sites should be selected whenever any of the following situations apply:

- a) Non-VCU sites that will be collaborating on a VCU-led study (i.e. involved in conducting the research, including being involved in the study interpretation or analysis of data and/or authorship of presentations or manuscripts related to the research.)
- b) Non-VCU sites that will be deferring to the VCU IRB for IRB review
- c) Non-VCU sites where VCU investigators will be overseeing study interventions or interactions
- d) Non-VCU sites/locations where VCU investigators will conduct study activities

2. * Select any of the following non-VCU sites utilized in this study:

- McGuire VAMC
- Foreign Sites
- Other Non-VCU Sites
- No Non-VCU Sites

3. * Is this a multi-center study being led by VCU?

Yes No

4. * For Non-VCU Sites: For each site or institution listed as "Site Engaged -- Requests to Rely on VCU IRB Review," upload:

- Completed Local Context Form for Relying on VCU's IRB
- Site specific informed consent form(s) and HIPAA authorization(s), if applicable

For Foreign Sites: For each Cultural Consultant upload a CV/Biosketch that includes a clear description of cultural expertise:

Document Name	Document	Version	Date Modified	Uploaded By	Type	Approved
View Version 3_Weight Blanket Study Consent Form_5-23-2024_Clean.docx	Version 3_Weight Blanket Study Consent Form_5-23-2024_Clean.pdf	0.03	6/7/2024 1:56 PM	[name]	Consent/Assent/Information Sheet	Yes
View Version 3_Weight Blanket Study Consent Form_5-22-2024_Redlined.docx	Version 3_Weight Blanket Study Consent Form_5-22-2024_Redlined.docx	0.01	5/22/2024 3:53 PM	[name]	Consent/Assent/Information Sheet	Yes
View Consent Form	Weight Blanket Study Consent Form_10-11-2023 - Copy - Copy.pdf	0.04	10/11/2023 11:35 AM	[name]	Consent/Assent/Information Sheet	Yes
View Weighted Blanket Device Information	Weighted Blanket Info for IRB_07 27 2023.docx	0.02	7/27/2023 10:29 AM	[name]	Other	Yes
View Data Collection Spreadsheet	Weighted Blanket Data Spreadsheet 5 23 2023.xlsx	0.01	5/23/2023 11:02 AM	[name]	Other	Yes
View Patient Participant Experience Survey	Weighted Blanket Participant Survey 5 23 2023.pdf	0.01	5/23/2023 11:02 AM	[name]	Research Measure	Yes
View Legally Authorized Representative (LAR) Experience Survey	Weighted Blanket Legally Authorized Representative Survey 05 23 2023.pdf	0.01	5/23/2023 11:02 AM	[name]	Research Measure	Yes

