Daily screening for inclusion/exclusion criteria will be conducted by the research team for patients admitted to VCUMC Medical Respiratory ICU (MRICU) and CMH ICU via EHR bedboards (via Epic) for both sites. For VCU Medical Center patients meeting inclusion criteria, a member of the study team will approach the patient at the bedside to review the informed consent form and answer any questions the patient may have before signing the consent. If the patient is not alert and oriented (as determined by the most recent physical assessment in the EHR and verified by the study team member bedside when engaging with the patient), the patient's LAR will be approached for consent, either in person in the intensive care unit (in the patient's room or in the dedicated family conference room to provide for privacy), or by phone (via number for LAR in EHR) if not available in person. The informed consent form will be reviewed with the LAR and questions answered by a member of the study team before signing. If the LAR does not answer when called, a message will be left via voicemail indicating that their family member may be eligible for participation in a clinical research study. They will be asked to call the study team member back at their convenience. If the LAR does not call back that day, a member of the study team will reach back out the next day. Failure to return a second message before the end of that day will indicate the desire to not have their family member participate and the LAR will not be contacted any further. The same procedures will occur for patients at CMH that meet study criteria. However, all in-person interactions planned for the VCU Medical Center site will be transferred to electronic means via Zoom. The designated study team member at CMH will bring the study dedicated iPad to the patient's bedside to engage with patients and/or their LAR. If the LAR desires, there will also be a dedicated private room at CMH where LARs can engage with the study team member reviewing the consent via Zoom. Although LAR consent will be required for enrollment of patients that are not alert and/or oriented, patient assent will be sought whenever possible.

5. * Does this study have a separate protocol document (i.e. a multisite or sponsor's protocol) that contains a detailed description of the study's methodology?

- Yes
 No

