 Research Assistant
 Pharmacist
 Statistician

- Regulatory Coordinator

- Trainee/Student(working on project)

- Other

- N/A: Requesting Waiver of Consent

7. * Describe the consent procedures used for this group. Address each point below:

- **When and where consent will occur**
- **What will be covered during the consent discussion**
- **How the consent discussion will occur (e.g. in-person, phone, video conference)**
- **How you will reconfirm consent on an ongoing basis, if applicable**

At the VCU Health Medical Center Main Hospital, the informed consent process will occur in an in-patient (bedside or unoccupied family conference room) or telephone setting. If the patient is decisionally competent (alert and oriented), the patient will be approached. If the patient is decisionally impaired in any capacity, the legally authorized representative (LAR) will be approached for consent. In that case, the patient will give a signed, verbal, or other indication of assent, if possible. During the informed consent process, an unbiased review of the trial and consent form will be discussed. It will be stated that the patient will continue to receive standard of care, with or without consenting for the voluntary trial. A physical copy of a consent form will be used. If the LAR is not available in person, the consent discussion may occur via telephone.

At the VCU Health Community Memorial Hospital, consent will in the same manner as it will at the VCU Medical center but all in-person activities will occur using remote technology (i.e., Zoom). A designated study team member at the CMH site will provide the patient and/or their LAR a study-specific iPad so that the study team member conducting the ICF process can speak with them using live communication via Zoom. The CMH team member will provide the patient and/or LAR a physical copy of the ICF to review during the discussion. If the patient and/or LAR agree to enroll the patient, they will sign the form and will give it to the CMH study team member who will place it in a locked cabinet at CMH dedicated for the study until it is transported by the study PI or Co-I to the study office at VCU Medical Center.

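### A representative's silence is read as refusal, possibly before the 72-hour window closes, and no capacity re-check is written for a patient still waiting on that route

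*Combined protocol and SAP*

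**What the plan says.** **Who decides.** Under Consent Groups (Patient Participant), Q7: "If the patient is decisionally competent (alert and oriented), the patient will be approached". Under Decisionally Impaired Adults, Q6: "Consent will be sought from the patient's LAR when the patient is not able to fully consent for themselves".

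**How capacity is judged.** Two sections describe this.
- Study Procedures, Q4 says that a status of not alert and oriented is "as determined by the most recent physical assessment in the EHR and verified by the study team member bedside when engaging with the patient", and the LAR is approached after that.
- Decisionally Impaired Adults, Q3 starts from the chart: "Per the EHR, is the patient alert and orientated? If yes, the study team member obtaining consent will proceed to the patient's bedside". It writes no branch for a negative chart entry. Its confirmation step works in one direction only: "If there are ever any doubts, the LAR will be sought for primary consent with patient assent".

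**How an absent LAR is handled.** Under Study Procedures, Q4, a voicemail is left and a second contact follows the next day. Then: "Failure to return a second message before the end of that day will indicate the desire to not have their family member participate". The LAR is not contacted again.

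**The time allowed.** Study Procedures, Q6 sets enrolment within 72 hours of ICU admission. Consent Groups (Patient Participant), Q10 gives the patient or LAR as long as possible to decide, up to that limit.

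**Change in capacity.** Decisionally Impaired Adults, Q2 allows for recovery: "Decisional impairment for ICU patients may be temporary (i.e., resolves when sedating medication is decreased or removed". The same sentence adds that impairment may also be permanent. Repeated assessment appears in Q5 of that section, as continual assent during the study, and in Consent Groups, Q11, where it is limited to enrolled patients.

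**The concern.** The LAR rule turns non-contact into a decision about the patient, and it can do so while the patient is still eligible and may be recovering. Nothing written prompts the team to look at that patient's capacity again.

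Two things are at stake. First, a patient who could decide may never be asked. Second, feasibility and acceptability are the main aims, so recruitment and refusal counts are results in their own right. Recording an unreached LAR as a refusal mixes unavailability with unwillingness. If LARs are harder to reach at one hospital, the planned comparison of VCUMC with CMH carries that difference as though it were a difference in willingness. The affected patients may also belong to the group at highest risk of delirium, which Decisionally Impaired Adults, Q2 describes as essential to the aims.

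**Working it through.** The plan gives no figure to reproduce. The check is a timeline, a reading of the relevant sections side by side, and a test of whether the size can be estimated.

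**1. When the LAR route closes**

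Let *h* be the hours from ICU admission to the first message, and *c* the clock hour of that message (0 to 24). The documents give neither. I take the end of the day to be midnight; if it means the end of the staff day, closure comes earlier.

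- Closure, in hours after admission = *h* + (48 − *c*)
- Window left = 72 − closure = 24 + *c* − *h*

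| Case | Closure | Window left |
|---|---|---|
| *h* = 4, *c* = 12 (noon) | 4 + 36 = hour 40 | 72 − 40 = 32 h |
| *h* = 0, *c* = 24 | 0 + 24 = hour 24 | 48 h |
| *h* = 24, *c* = 0 | 24 + 48 = hour 72 | 0 h |

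For first messages sent in the first 24 hours, between 48 and 0 hours remain. The gap vanishes once *h* reaches 24 + *c*, which lies between hour 24 and hour 48 depending on the clock time. Early closure is therefore possible but not universal.

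**2. Whether any section fills the gap**

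- *Daily screening* (Study Procedures, Q4) covers inclusion and exclusion criteria. Those listed under Study Population, Q4 and Q5 do not include current orientation or capacity, so repeat screening does not by itself prompt a capacity check.
- *Continual assent* covers enrolled patients and does not reach someone awaiting an LAR's reply.
- *The rule on competent patients* (Consent Groups, Q7) gives no time for re-assessment and does not mention a case in which the LAR has already been closed out.
- *The decision time* (Consent Groups, Q10) runs to hour 72, whereas Study Procedures, Q4 can end it sooner.

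**3. Bedside verification**

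Study Procedures, Q4 verifies a negative status at the bedside. Decisionally Impaired Adults, Q3 sends the team to the bedside only on a positive chart entry. Staff following the second section alone could go to the LAR on the chart entry.

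**4. Size**

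Share affected = P(LAR needed) × P(LAR not reached) × P(capacity regained within 72 hours). All three rates are assumptions.

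- Low: 0.40 × 0.20 × 0.10 = 0.8%
- Middle: 0.60 × 0.30 × 0.30 = 5.4%
- High: 0.70 × 0.40 × 0.50 = 14%

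Study Population, Q3 supports two denominators. The cited 53% non-participation gives 50 / 0.47 ≈ 106 approached. The plan's own allowance gives 50 + 75 = 125.

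| Denominator | Low | Middle | High |
|---|---|---|---|
| 106 | 0.8 | 5.7 | 14.8 |
| 125 | 1.0 | 6.8 | 17.5 |

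The product counts every recovery within 72 hours. Only recoveries after closure and before hour 72 fall squarely in the gap, so each result must be multiplied by an unknown fraction no greater than 1. The counts are also missed approaches, not lost enrolments, because some of these patients would decline.

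**The case against.** The strongest reply is that the plan, read as a whole, permits approaching a patient who wakes and arguably calls for it. A competent patient is to be approached, the LAR is used only when the patient cannot fully consent, the chart entry relied on is the most recent one, and the decision period runs to hour 72. What Q4 expressly ends is contact with the LAR.

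Much of this stands, and it rules out several stronger readings that a reader might infer:

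- *That a chart entry alone hands the decision to the LAR.* Study Procedures, Q4 requires a status "verified by the study team member bedside when engaging with the patient". The capacity section omits this step for a negative entry but does not say to skip it.
- *That a single voicemail closes the case.* It takes two contact attempts over two days.
- *That a patient who wakes is barred from being asked.* No text says so.
- *That impairment usually resolves.* The plan says only that it may be temporary.

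The consequence is also limited. This is a descriptive pilot in a convenience sample of 50, and a patient who is not enrolled continues standard care. Review Setup shows a continuing-review category for studies with only data analysis remaining, so recruitment text may no longer govern new patients.

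The reply does not remove the rule itself. Reading silence as a wish not to take part is a stated interpretation, it can take effect before the window ends, and no section says how it gives way when the patient recovers.

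**Conclusion.** The point holds as an early-closure rule combined with a silence and an inconsistency. LAR non-response is treated as unwillingness at the end of the day after the first message, which can precede hour 72. No capacity re-check is described for a patient not yet enrolled. Whether the rule on competent patients still applies after closure is left open, so staff at two hospitals could act differently, and a patient who regains capacity may be recorded as declined without being asked. Separately, the two accounts of bedside verification need reconciling.

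The timeline rests on the assumed time of the first message; with a late first message the problem disappears. The number of patients affected cannot be estimated from the documents. The 5.4% is illustrative, rests on three assumed rates and is an upper bound on those inputs. It should not be reported as an expected loss. The change is worth making because it is cheap and protects both the patient's own decision and the meaning of the refusal count.

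**What to change.** 1. In Decisionally Impaired Adults, Q3, match Study Procedures, Q4: verify capacity at the bedside whichever way the chart reads.
2. State that capacity is re-checked at each daily screen until hour 72 for any patient on the LAR route who is not yet enrolled.
3. State that a patient who regains capacity in the window is approached directly, unless the LAR has actually declined.
4. In Study Procedures, Q4, treat LAR non-response as final only when the 72-hour window ends, in line with Consent Groups, Q10. No extra calls to the LAR are needed.
5. Log these cases as *representative not reached*, separate from refusal, and report the two counts by hospital.

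The cost is a few sentences and a few more patient approaches. Daily screening already takes place, though it runs from the chart, so the re-check adds some short bedside visits (by Zoom at CMH). If enrolment here has ended, item 5 still applies to reporting wherever the log allows the two reasons to be separated. The remaining items then belong in the larger randomized trial that this pilot is meant to support.
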